3.1.1 Administrative structure of the trial

Boehringer Ingelheim (BI), the sponsor of this trial, has appointed a Trial Clinical Monitor, responsible for coordinating all required activities, in order to

- manage the trial in accordance with applicable regulations and internal SOPs,
- direct the clinical trial team in the preparation, conduct, and reporting of the trial,
- order the materials as needed for the trial,
- ensure appropriate training and information of local clinical monitors (CML), Clinical Research Associates (CRAs), and Investigators of participating countries.

The sponsor will designate appropriately qualified personnel to advice on trial-related topics.

Data Management and Statistical Evaluation will be done by BI according to BI SOPs.

A list of responsible persons and relevant local information (as protocol reference, if applicable) can be found in the ISF and the Clinical Trial Master File (CTMF).

A Coordinating Investigator will be nominated and will be responsible to coordinate Investigators at different centres participating in this multicentre trial. Tasks and responsibilities will be defined in a contract. Relevant documentation on the participating (Principal) Investigators and other important participants, including their curricula vitae, will be filed in CTMF.

A central laboratory service and an IRT vendor will be used in this trial. Details will be provided in IRT Manual and Central Laboratory Manual, available in the ISF.

Proprietary confidential information © 2016 Boehringer Ingelheim International GmbH or one or more of its affiliated companies

3.2 DISCUSSION OF TRIAL DESIGN, INCLUDING THE CHOICE OF CONTROL GROUP(S)

The study design of this trial is based on the Guideline on Clinical Development of Fixed Combination Medicinal Products of the EMA's Committee for Medicinal Products for Human Use (CHMP) [R09-2704]. The design is suited to assess the effect of a gel containing diclofenac and capsaicin on acute back or neck pain compared with gels containing the individual components, diclofenac or capsaicin, or placebo. Comparison with the individual components is necessary to confirm a clinically meaningful effect of the combination in terms of pain relief. Comparison with placebo is necessary to assess the overall relative effect of the combination of diclofenac and capsaicin.

Assessment of pain at rest provides important information on patients comfort during treatment [P08-09626]. However, for measurement of pain at rest patients tend to move into a relieving posture which limits the value of the measurement to reflect patient's restriction in performing daily activities. Other than at rest, functional limitations become obvious during movement. Functional improvement can be detected by standardized movements [R14-1467]. Thus, POM was selected as the primary variable for assessment of pain relief. For back and neck pain standardized movements have been established [R14-1467, R12-4427].

For the assessment of the primary endpoint, POM_{WP} 1 hour after the evening application on Day 2 will be compared to POM_{WP} at baseline. Typically a treatment effect of topical treatments can be observed after 1 to 3 days. The chosen time frame for assessment of the primary endpoint allows sufficient time for the trial treatment to become effective. On the other hand it is sufficiently short to avoid diminishing differences by the self-limiting properties of acute back or neck pain. Similar time frames were chosen in comparable clinical trials [R14-1467, R12-4427].

3.3 SELECTION OF TRIAL POPULATION

A sufficient number of patients with acute back or neck pain will be screened. It is assumed that approximately 800 patients will need to be randomized at around 20 trial sites to achieve 700 patients who are evaluable with regard to the primary endpoint.

It is expected that around 40 patients will be randomised at each trial site. If enrolment is delayed, additional sites may be recruited. Permission to randomise more than 80 patients per site must be obtained from the Trial Clinical Monitor (TCM) at BI. This will only be allowed after a careful review of the enrolment status and of the site.

Screening of patients for this trial is competitive across all countries and sites within the trial, i.e. screening for the trial will stop at all sites when it is anticipated that a sufficient number of patients have been screened to yield the desired number of patients randomised to trial treatment. Investigators will be notified when sufficient patients have been screened and when screening is complete, and will not be allowed to recruit additional patients for the study.

Trial Protocol

c03317678-02 Page 20 of 69

Proprietary confidential information © 2016 Boehringer Ingelheim International GmbH or one or more of its affiliated companies

A log of all patients enrolled into the trial (i.e. who have signed informed consent) will be maintained in the ISF at the investigational site irrespective of whether they have been treated with investigational drug or not.

3.3.1 Main diagnosis for trial entry

Only patients with acute neck or back pain will be screened for suitability for the study.

Please refer to Section 8.3.1 (Source Documents) for the documentation requirements pertaining to the in- and exclusion criteria.

3.3.2 **Inclusion criteria**

- 1. Signed and dated written informed consent at Visit 1 in accordance with Good Clinical Practice (GCP) and local legislation.
- 2. Male or female patients ≥ 18 years with current diagnosis of acute back pain or of neck pain for at least 24 hours, but less than 21 days.
- 3. Acute back pain or acute neck pain resulting in pain on movement (POM) \geq 50 mm (VAS 0-100) for at least one POM procedure out of 5 standardized procedures.

The POM measurement with the highest pain response will determine if the patient has back or neck pain (see Section 5.2.1 for further details).

- 4. Sensitivity to algometric pressure on the painful trigger point < 25 N/cm² (see Section 5.2.2).
- 5. Women of childbearing potential* must be ready and able to use highly effective methods of birth control per ICH M3(R2) that result in a low failure rate of less than 1% per year when used consistently and correctly. A list of contraception methods meeting these criteria is provided in the patient information.
 - *Women of childbearing potential are defined as:

Any female who has experienced menarche and does not meet the criteria for "women not of childbearing potential" as described below.

Women not of childbearing potential are defined as:

Women who are postmenopausal (12 months with no menses without an alternative medical cause) or who are permanently sterilized (e.g. tubal occlusion, hysterectomy, bilateral oophorectomy or bilateral salpingectomy).

c03317678-02 Page 21 of 69

Proprietary confidential information © 2016 Boehringer Ingelheim International GmbH or one or more of its affiliated companies

3.3.3 **Exclusion criteria**

- 1. History of 3 or more episodes of back or neck pain in the last 6 months excluding the current episode
- 2. Surgery due to back or neck pain or rehabilitation due to back or neck pain in the last 12 months
- 3. Back or neck pain that is attributable to any specific identifiable cause (e.g. disc prolapse, spondylolisthesis, osteomalacia, inflammatory arthritis, metabolic, neurological diseases or tumour).
- 4. Trauma or strains of the back or neck muscles within the last 3 months.
- 5. Prior use within the last 3 days before Visit 1 or concomitant use of any antiinflammatory drugs, heparinoids, muscle relaxants or analgesics (including but not limited to short-acting glucocorticoids, non-steroidal anti-inflammatory drugs [NSAIDs], herbal preparations).

Long-acting glucocorticoids must have been discontinued 10 days before study entry.

Spinal injections should have been discontinued in due time (investigator's judgement) before patient enrolment to allow complete wash-out of the active ingredient based on investigator's judgment.

Exceptions: Acetyl salicylic acid (ASS) up to 100 mg/day for cardiovascular therapy, antidepressants or antipsychotics on stable dose for at least 2 weeks prior to Visit 1. Use of inhaled glucocorticoids (e.g. for asthma or chronic obstructive pulmonary disease) is acceptable.

- 6. Non-pharmacological treatment (physiotherapy, heat treatment (e.g. heat patch, hot water bottle), or massage, acupuncture, transcutaneous electrical nerve stimulation [TENS]) or locally applied pharmacological product to the back or neck area 24 hours prior study entry and during the study period.
- 7. Known severe hepatocellular insufficiency, severe renal insufficiency or Gilbert's syndrome (Morbus Meulengracht)
- 8. Any other medical condition that would interfere with efficacy and safety assessments based on investigator's judgement or any on-going clinical condition that would jeopardize patient's or site personnel's safety or study compliance based on investigator judgement.

Proprietary confidential information © 2016 Boehringer Ingelheim International GmbH or one or more of its affiliated companies

- 9. Known intolerance or hypersensitivity to the active ingredients or any excipient(s).
- 10. Patients in whom attacks of asthma, bronchospasm, rhinitis or urticaria were precipitated by the intake of ASS or other NSAIDs
- 11. Irritated skin (based on investigator's judgement), skin wounds, eczema or open injuries at application site (the trial medication should only be applied to intact, non-diseased skin)
- 12. Negative experience in the past with heat treatments for muscle complaints (e.g. heat pads, hyperaemisations inducing topical creams, gels, ointments, patches)
- 13. Patient not able to understand and comply with trial requirements based on investigators judgement
- 14. Alcohol or drug abuse within 3 months prior to Visit 1 that would interfere with trial participation based on investigator's opinion.
- 15. Participation in a clinical trial within the previous 30 days before enrolment in the trial, participation in this study before or simultaneous participation in another clinical trial.
- 16. Women who are pregnant, nursing, or who plan to become pregnant while in the trial (see also Section 4.2.2.3).

3.3.4 Removal of patients from therapy or assessments

3.3.4.1 Removal of individual patients

An individual patient is to be withdrawn from trial treatment if:

- The patient withdraws consent for study treatment or study participation, without the need to justify the decision.
- The patient needs to take concomitant drugs that interfere with the investigational product (see Section 3.3.3) or other trial medication. See Section 4.2.2 for further details.
- The patient can no longer be treated with trial medication or rescue medication for other medical reasons (such as surgery, adverse events, other diseases, or pregnancy)

If a patient becomes pregnant during the trial the study medication will be stopped, the patient will be discontinued from the trial and the patient will be followed up until birth or otherwise termination of the pregnancy.

Trial Protocol

c03317678-02 Page 23 of 69

Proprietary confidential information © 2016 Boehringer Ingelheim International GmbH or one or more of its affiliated companies

A patient can be discontinued after discussion between Sponsor and Investigator if eligibility criteria are being violated, or if the patient fails to comply with the protocol (e.g. nonattendance at study assessments).

Patients who drop out during the screening prior to randomisation will be considered screening failures. They will be recorded as screening failures in the eCRF and no further follow-up is required. The data will be included in the trial database and will be reported.

Patients who discontinue or withdraw from the study after randomisation will be considered as "early discontinuations" and the reason for this premature discontinuation must be recorded in the eCRF. The Investigator must inform the sponsor within 24 hours via IRT (see Section 4.1) about any premature discontinuation of a subject. The data will be included in the trial database and will be reported. Given the patient's agreement, the patient will undergo the procedures for early treatment discontinuation and follow up (Visits 6 and 7T) as outlined in the Flow Chart and Section 6.2.3.

For all patients the reason for withdrawal (e.g. adverse events) must be recorded in the eCRF. These data will be included in the trial database and reported.

Discontinuation of the trial by the sponsor 3.3.4.2

Boehringer Ingelheim reserves the right to discontinue the trial overall or at a particular trial site at any time for the following reasons:

- 1. Failure to meet expected enrolment goals overall or at a particular trial site
- 2. Emergence of any efficacy/safety information invalidating the earlier positive benefitrisk-assessment that could significantly affect the continuation of the trial
- 3. Violation of GCP, the Clinical Trial Protocol (CTP), or the contract disturbing the appropriate conduct of the trial

The Investigator / the trial site will be reimbursed for reasonable expenses incurred in case of trial termination (except in case of the third reason).

c03317678-02 Trial Protocol Page 24 of 69

Proprietary confidential information © 2016 Boehringer Ingelheim International GmbH or one or more of its affiliated companies

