3. DESCRIPTION OF DESIGN AND TRIAL POPULATION

3.1 OVERALL TRIAL DESIGN AND PLAN

This trial is a prospective, randomised, double-blind, parallel group, multi-centre trial to show superiority in terms of reduction of Pain on Movement (POM) of a topical combination containing diclofenac 2% and capsaicin 0.075% compared to placebo, as well as to diclofenac 2% and capsaicin 0.075% when applied twice daily over 4 to 7 days to patients with acute back pain or neck pain. A total of approximately 800 patients will be randomised to the treatment groups diclofenac + capsaicin, diclofenac, capsaicin and placebo in a 3:3:3:1 ratio in order to achieve 700 patients eligible for the assessment of the primary endpoint.

After a screening evaluation (Visit 1), eligible patients will be randomised into the double-blind treatment phase of the trial. After administration of the first treatment, the patients will administer the second application of the trial medication in the evening at home. They will return to the trial site for four more visits (Visits 2 to 5) in the morning and in the evening of the following day (Day 2) and in the morning of Days 3 and 4 and thereby be dosed while at the site. Evening applications on Day 3 and Day 4 will be administered by the patients at home. Thereafter, the treatment will be administered at home for one more day (Day 5). The patients will then return to the trial site for final assessments (Visit 6) in the morning of Day 6. The trial participation will be concluded by a telephone call (Visit 7T) for follow-up on adverse events (AEs) on Day 8.

Depending on the severity of a patient's condition and on a patient's availability, the treatment-period at home (Day 5) could be skipped or extended by one or two days. Visit 6 should then be performed on the day immediately following to that shortened or extended period.

The interval between two applications of the trial medication should be 12 hours. This interval could be shortened or extended by 4 hours as long as no more and no less than two applications are administered on each treatment day.

Patients who discontinue the application of the trial medication prematurely, should be encouraged to contact the site immediately so that Visits 6 and 7T could be performed on the day immediately after discontinuation.

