5.3.7 Adverse event collection and reporting

AE Collection

The Investigator shall maintain and keep detailed records of all AEs in their patient files. The following must be collected and documented on the appropriate eCRF by the Investigator (see also Figure 5.3.7: 1):

From signing the informed consent onwards through the Residual Effect period (REP), all AEs (serious and non-serious), and AESIs must be reported. However, if an individual patient discontinues trial medication prematurely but stays in the trial (i.e. if further visits including

Trial Protocol Page 42 of 69

Proprietary confidential information © 2016 Boehringer Ingelheim International GmbH or one or more of its affiliated companies

telephone visits, or vital status assessments are planned) from then on and until the individual patient's end of the trial the Investigator must report related SAEs and related AESIs.

[figure not shown]

Figure 5.3.7: 1 Graphical depiction of the requirements for AE collection

The REP is defined as 48 hours after the last trial medication application. All AEs which occurred through the treatment phase and throughout the REP will be considered as on treatment please see Section 7.3.4. Events which occurred after the REP will be considered as post treatment events.

After the last per protocol contact the Investigator does not need to actively monitor patients for AEs. However, if the Investigator becomes aware of SAEs or AESIs that occurred after the last per protocol contact, the SAEs and AESIs should be reported by the Investigator to the Sponsor if considered relevant by the Investigator.

AE reporting to sponsor and timelines

The Investigator must report SAEs, AESIs, and non-serious AEs which are relevant for the reported SAE or AESI, on the BI SAE form via fax immediately (within 24 hours) to the Sponsor's unique entry point (country specific contact details will be provided in the ISF). The same timeline applies if follow-up information becomes available. In specific occasions the Investigator could inform the Sponsor upfront via telephone. This does not replace the requirement to complete and fax the BI SAE form.

With receipt of any further information to these events, a follow-up SAE form has to be provided. For follow-up information the same rules and timeline apply as for initial information.

Information required

For each AE, the Investigator should provide the information requested on the appropriate

Trial Protocol

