6.2.3 Follow Up Period and Trial Completion

All study procedures according to the Flow Chart should be performed.

Patients who want to discontinue the trial treatment prematurely should be asked to have Visit 6 in the morning after the last application of the trial medication and to have a Visit 7T at least 48 hours after that last application.

Patients who at the end of their trial participation still require treatment for the trial indication should be treated according to local standard of care.

Proprietary confidential information © 2016 Boehringer Ingelheim International GmbH or one or more of its affiliated companies

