The key secondary endpoints as outlined in Section 5.1.2 will be analysed hierarchically $(POM_{WP}AUC_{72} \text{ first})$ in a confirmatory way only, if statistical significance was achieved for the primary endpoint. Therefore, no alpha-adjustment for multiple endpoint testing will be applied.

All other secondary endpoints as outlined in Section 5.1.3 will be considered as supportive only.

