5.2 SECONDARY ENDPOINTS

5.2.1 Key secondary endpoints

• POM_{WP}AUC₇₂ and POM_{WP}AUC₁₂₀

AUC will be calculated as area under the curve from zero to approximately 72 hours (corresponding to $POM_{WP, day 4 \text{ morning post application}}$) or to approximately 120 hours (corresponding to $POM_{WP, day 6 \text{ morning}}$) using the trapezoidal rule divided by the observation time.

$$POM_{WP}AUC_{72} = \frac{1}{t_6} \sum_{i=1}^{6} \frac{1}{2} (POM_{WP}(t_{i-1}) + POM_{WP}(t_i)) * (t_i - t_{i-1})$$

$$POM_{WP}AUC_{120} = \frac{1}{t_7} \sum_{i=1}^{7} \frac{1}{2} (POM_{WP}(t_{i-1}) + POM_{WP}(t_i)) * (t_i - t_{i-1})$$

Study drug application date/times will be the basis for the calculation of respective time intervals.

 $t_0 = 0$,

for i=1 to 6,

 $t_i = ([actual date of application of POM_{WP} assessment i+1] - [actual date of first application (visit 1)]) * 24 + [actual time of application of POM_{WP} assessment i+1] - [actual time of first application (visit 1)] + 1_{post-value}.$

 $t_7 = ([actual date of application on Day 5 evening] - [actual date of first application (visit 1)]) * 24 + [actual time of application on Day 5 evening - actual time of first application (visit 1)] + 12.$

where

$$1_{post-value} = \begin{cases} 0, if \ pre-application \ POM_{WP} \ value \\ 1, if \ post-application \ POM_{WP} \ value \end{cases}$$

Planned assessment times are:

Assessment	t _i
1 (Baseline)	$t_0 = 0$
2 (Day 1 morning, 1 hour after application)	t ₁ = 1
3 (Day 2, morning, 1 hour after application)	$t_2 = 25$
4 (Day 2 evening, before application)	$t_3 = 36$
5 (Day 2 evening, 1 hour after application)	$t_4 = 37$
6 (Day 3, morning, 1 hour after application)	$t_5 = 49$
7 (Day 4, morning, 1 hour after application)	$t_6 = 73$
8 (Day 6, morning)	$t_7 = 120$

For AUC calculation, one or more missing assessments in between POM assessments will be imputed using the planned assessment time and a linear interpolation of the last available assessment before (including baseline, if applicable) and the first available assessment after the missing assessment. If there is no evaluable assessment after the planned time of the missing assessment, planned assessment time and LOCF will be used to impute the value.

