6.7 BASELINE, TIME WINDOWS AND CALCULATED VISITS

Definition of baseline

Baseline values are defined as the last morning assessment prior to randomization and the first drug application on day 1 (Visit 1).

Time windows

Time windows for visits are shown in the Flow Chart in the CTP. Visits 1-5 must be carried out on the specified days, for Visit 6 there is a time window of -1/+2 days, for Visit 7T there is a time window of +4 days.

Calculated visits

Visits which occur outside of the defined visit window are flagged as PVs.

If a single scheduled visit is completed outside of the visit window, as defined in the CTP, that visit will be assigned to the scheduled visit. For example, if a patient completes a visit in the afternoon of day 3, the visit would be assigned to visit number 4.

If two consecutive scheduled visits are missed, but a single visit completed between the visit for both scheduled (but missed) visits, the completed visit will be assigned to the closest scheduled visit. However, the final assignment of the visit should be agreed at a medical quality review meeting (MQRM) or BRPM.

Unscheduled visits are not expected for this study. However, should unscheduled visits occur between non-missed scheduled visits, they are assigned separate visit numbers according to BI convention, but will not be included in the summary statistics and will not be used in any inferential analysis.

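### A treated, attending patient can be discontinued for an eligibility or compliance deviation, and part of that patient's confirmatory AUC72 and AUC120 is then imputed although the scores could have been measured

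*Protocol*

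**What the plan says.** Protocol Section 3.3.4.1 first lists grounds for withdrawal from treatment: consent withdrawn, interfering medication, medical reasons. It then adds a discretionary ground: "A patient can be discontinued after discussion between Sponsor and Investigator if eligibility criteria are being violated, or if the patient fails to comply". Its example of non-compliance is nonattendance. If the patient agrees, "the patient will undergo the procedures for early treatment discontinuation and follow up (Visits 6 and 7T"). Section 3.1 asks such patients to contact the site at once "so that Visits 6 and 7T could be performed on the day immediately after discontinuation", and Section 6.2.3 says that they "should be asked to have Visit 6 in the morning after the last application of the trial medication". No section schedules the remaining pain on movement (POM) visits. Section 5.3.7 does foresee the case "if an individual patient discontinues trial medication prematurely but stays in the trial", but only for adverse event reporting.

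AUC72 and AUC120 are the key secondary endpoints, tested in that order "in a confirmatory way only, if statistical significance was achieved for the primary endpoint" (Protocol Section 7.2). SAP Section 7.5.1 analyses them on the treated set. SAP Section 5.2.1 interpolates gaps between two available scores; where no later score exists, "planned assessment time and LOCF will be used to impute the value".

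SAP Section 6.7 has two rules for visits outside their window. A single such visit goes to its own scheduled visit. Where two consecutive visits were missed and one visit took place between them, "the completed visit will be assigned to the closest scheduled visit", subject to agreement at a review meeting.

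**The concern.** Removal does not take the patient out of the AUC analyses. It swaps scores that could have been collected at visits already planned for values generated by interpolation or carry-forward. Protocol Section 3.2 describes the pain as self-limiting, so a score carried from 25 h to 73 h is a weak substitute for an observation.

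A second gap concerns every early leaver. The early Visit 6 falls on Day 3 or Day 4, outside the window of -1/+2 days around Day 6. The single-visit rule of SAP Section 6.7 then makes it assessment 8, planned at 120 h. The time of that assessment is computed from the Day 5 evening application plus 12 h, or from the Day 5 morning application plus 24 h (SAP Sections 4 and 5.2.1). A patient removed on Day 2 or Day 3 has neither. The plan thus gives no valid time for a score that was actually taken at about 48 h or 72 h.

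**Working it through.** The documents state no imputed share and no expected number of such removals, so there is no figure of the plan to reproduce. The inputs are the planned assessment times in SAP Section 5.2.1: 0, 1, 25, 36, 37, 49, 73 and 120 h.

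**Weights.** Under the trapezoidal rule an inner point has weight (next time - previous time)/2, and an end point has half of its one interval.

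- AUC72: 0.5, 12.5, 17.5, 6, 6.5, 18, 12; sum 73.
- AUC120: 0.5, 12.5, 17.5, 6, 6.5, 18, 35.5, 23.5; sum 120.

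Imputed share = sum of the weights at unmeasured times / total weight.

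**Cases.** All scores up to the removal visit are measured. The early Visit 6 takes place the next morning: Day 3 after Visit 2 or Visit 3, Day 4 after Visit 4. Its score is placed at the closest planned time, placed at 120 h, or not used.

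| Removed after | Early Visit 6 score | AUC72 imputed | AUC120 imputed |
|---|---|---|---|
| Visit 2 | at 49 h | (6+6.5+12)/73 = 24.5/73 = 34% | (6+6.5+35.5+23.5)/120 = 71.5/120 = 60% |
| Visit 2 | at 120 h | (6+6.5+18+12)/73 = 42.5/73 = 58% | 66/120 = 55% |
| Visit 2 | not used | 42.5/73 = 58% | 89.5/120 = 75% |
| Visit 3 | at 49 h | 12/73 = 16% | 59/120 = 49% |
| Visit 3 | at 120 h | (18+12)/73 = 30/73 = 41% | 53.5/120 = 45% |
| Visit 3 | not used | 30/73 = 41% | 77/120 = 64% |
| Visit 4 | at 73 h | 0% | 23.5/120 = 20% |
| Visit 4 | at 120 h | 12/73 = 16% | 35.5/120 = 30% |
| Visit 4 | not used | 12/73 = 16% | 59/120 = 49% |

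The rows at 120 h count a score taken on Day 3 or Day 4 as a measured 120 h value, so their AUC120 shares look better than they are. Removal before the Visit 2 score is not tabulated and would give larger shares.

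**What the 34% consists of.** The 36 h and 37 h points contribute 12.5/73 = 17%, interpolated between measured scores at 25 h and 49 h. Only 12/73 = 16% is carried forward. In the not-used case, the 25 h score alone carries (17.5+42.5)/73 = 60/73 = 82% of AUC72.

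**Arm level, under assumed rates.** Arm share = assumed share of the arm removed after Visit 2 × per-patient share, here for AUC72:

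- 1%: 0.3% to 0.6%
- 5%: 1.7% to 2.9%
- 12.5%: 4.2% to 7.3%. This is the protocol's whole allowance for non-evaluable patients, 100 of 800, and so an extreme bound.

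If the remaining visits are held and their times are defined, the imputed share is 0%.

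**The case against.** The rule is optional and applied case by case, and much of what it reaches is proper stopping. The exclusion criteria include hypersensitivity, NSAID-induced asthma, damaged skin, pregnancy and prohibited concomitant treatment. Missed visits are already covered: Protocol Section 6.1 keeps later visits on the original schedule. Section 6.2.1 makes a full eligibility check the last step before randomisation. What is left is a safe, attending patient removed for a formal deviation within about three days, and nothing suggests that this is common. All of this stands and narrows the point.

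It also stands that about half of the 34% is interpolation between nearby measured scores; the trapezoidal rule draws the same kind of straight line from 1 h to 25 h in every patient. The SAP's table of important protocol violations cannot be read in the public copy, so how deviations are classified must not be called missing.

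A further objection is aimed at the remedy. The SAP takes assessment times from gel application times, so a patient off the gel has no time for Visits 3 to 5, and using off-treatment scores is a choice about what the AUC should estimate. This is correct, and the fix has to carry its own timing rule. The plan does already analyse treated patients in their randomised group, so observed scores fit that choice better than imputed ones.

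None of this alters the fact that the text provides no POM visit after discontinuation other than the early Visit 6.

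**Conclusion.** The point holds as a cheap improvement, not as an error that threatens a conclusion. For one attending patient removed after Visit 2, 34% to 58% of the AUC72 weight is imputed, falling to 16% to 41% after Visit 3 and 0% to 16% after Visit 4. The upper ends follow from the literal reading of SAP Section 6.7. The figures assume visits at their planned times and no other missing scores.

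Three stronger readings are tempting, and the documents do not support them.

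- A reader might infer that a third or more of the AUC72 analysis rests on imputation. The shares are per removed patient; even 5% removed, an assumed rate, gives under 3% for the arm.
- A reader might infer a biased treatment contrast. Protocol Section 4.1.5.1 keeps everyone involved in conduct or analysis blinded until after database lock, and nothing shows that removals would differ by arm. No loss of power is shown either.
- A reader might infer that the primary endpoint is at risk. Both Visit 3 scores are lost if removal falls between Visit 2 and Visit 3, but that interval is only about 12 hours. The repeated measures model uses the earlier scores without imputation, so the effect is probably very small.

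**What to change.** 1. In Protocol Section 3.3.4.1, state that an eligibility or compliance deviation found after randomisation does not by itself end participation. The gel may still be stopped for safety, for medical reasons or because of prohibited medication. A willing patient continues the scheduled POM visits through Visit 6.
2. In the SAP, place an early Visit 6 POM score at the planned assessment closest to its actual time. For AUC points with no gel application, use the actual assessment time, or the planned time if the actual one was not recorded.

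The cost is one or two sentences in a protocol amendment and one or two in the SAP, with no new visits. The downside is that a few ineligible or poorly compliant patients are followed for a few more days, and some off-treatment scores enter the AUC. The SAP change is useful for anyone who leaves early, whatever the reason.
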